After single doses of 2–60 mg, BEN8744 demonstrated a shorter than expected elimination half-life, ranging approximately 2–4 h. At the highest dose tested (60 mg), mean C_{avg} was below IC_{90} . However, a single subject had a higher AUC_{inf} , approximately 2-fold above the mean and above IC_{90} . In all subjects after 60 mg BEN8744, plasma concentrations decreased below the IC_{50} by 11 h postdose. Considering the observed short half-life, and predicted required time above IC_{50} for efficacy in patients, a twice daily dosage regimen will be required in Part C (MAD Phase) to achieve exposures above IC_{50} for up to 18–24 h.

The impact of gut P-glycoprotein (P-gp) efflux and gut cytochrome p450 3A4 (CYP3A4) mediated metabolism was not expected to be significant in humans; however, emerging clinical data suggests there is an impact which is significant at lower doses. Between 2 and 6 mg QD the increase in PK parameters appeared dose-proportional, but escalation between 6, 20 and 60 mg QD resulted in a greater than proportional increase in AUC_{inf} , suggestive of non-linear PK. Additionally, between-subject variation was high. While the linear approach overpredicted exposures at low doses, the mean C_{max} and AUC_{inf} at 60 mg aligns with predicted exposures. Mean apparent clearance (CL/F) decreased with an increase in dose from 6 to 60 mg QD, which may indicate approaching saturation of gut P-gp and CYP3A4. Hence, at higher doses exposure is expected to be closer to dose-proportional.

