8.1.3 Part C

Enrolment of up to 32 healthy subjects is planned, in up to 3 groups (Groups C1–C3) and 1 optional group (Group C4). Each group will consist of 8 subjects.

Each subject will receive daily doses of BEN8744 or placebo, by mouth, for 14 days. At each dose level, 6 subjects will receive BEN8744 and 2 will receive matching placebo. Doses will be taken once or twice daily in the fasted state, unless emerging data indicate they should be taken in the fed state.

[figure not shown]
Part C will not start until at least 3 dose levels have been completed in Part A, as described in section 8.5.4. Part C may also be conducted in parallel with Part B. The dose, dosing regimen (once or twice daily), and whether the dose is taken fed or fasted, will be determined based on review of the available safety, tolerability and PK results from Parts A and B, and previous groups in Part C, as described in section 8.5.

The first total daily dose (ie, morning plus evening dose, if a twice-daily dosing regimen is chosen) tested in Part C (Group C1) will be the same as, or lower than, a single dose that has been given in Part A without any safety concerns. See also section 8.5.

[figure not shown]
[figure not shown]
[figure not shown]
Subjects will be screened within 28 days before their first dose of trial medication. Subjects will be resident on ward from the day before their dose (Day -1) until up to 72 h after their final dose (Day 17). They will return for a follow-up visit 7 (± 2) days after their inpatient stay (Day 24 ± 2 days).

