In Part C, we anticipate that doses will be given once or twice daily in the fasted state unless emerging data indicate they should be taken in the fed state. Fasting requirements in Part C will be decided by the SRG after review of results from Parts A and B. Therefore, for the morning dose, subjects will either:

- fast from midnight on the evening before each dose, until 4 h after their morning dose, on the first and last dosing days, and until 2 h after dosing on all other dosing days. Water will not be allowed for 1 h before and after dosing; or
- fast from midnight before each dose, until about 30 min before the morning dose on all dosing days. Subject will be given a standard breakfast to finish before dosing, consisting of 2 slices of toast, 1 bowl of cereal with semi-skimmed milk, 2 portions of butter/margarine, and 1 portion of jam. Water will not be allowed for 1 h before and after dosing.

In once-daily dosing sessions, standard meals and drinks will be provided at about 4 and 10 h after dosing on all dosing days, and at 24 h after the last dose on the final dosing day.

If subjects are dosed twice daily, they will take their evening doses approximately 1 h after dinner. Water will not be allowed for 1 h before and after dosing.

All parts

No food or drink containing cranberry, pomegranate, starfruit, grapefruit, pomelos, exotic citrus fruits or Seville oranges (including marmalade and juices made from these fruits) will be allowed from 14 days before (first) dosing until the end of the trial. No alcoholic or caffeinated drinks, or xanthine-containing products (eg chocolate) will be allowed during the period from 24 h before admission until the end of the period of residence, and for 24 h before each outpatient visit (including screening). Subjects should be advised to avoid eating food containing poppy seeds

from screening until the end of the study, because that can cause a positive drugs of abuse test result.

No strenuous exercise will be allowed from 24 h before admission, and for 48 h before each outpatient visit (including screening).

Regular smokers or users of tobacco and/or nicotine containing products (including e-cigarettes) are excluded from the study (see section 9.3). ‘Social’ smokers or vapers must abstain from smoking/vaping from 1 month before their first dose of study medicine until the end of the study.

Subjects must not sunbathe or use a sunbed during the study.

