12.1.3 Schedule of procedures (Part C)

	Screening ¹	Treatment session						Follow-up ²			
		Day -1	Day 1	Days 2-6	Day 7	Days 8-13	Day 14	Day 15	Day 16	Day 17	Day 24 ±2
Informed consent	X										
Demography	X	X									
Medical history	X										
Inclusion/exclusion criteria	X	X									
Height and weight ³	X	X									
Dose of BEN8744 or placebo ⁴			X		X		X		X		
Inpatient visit ⁵											
Outpatient visit	X										
Safety assessments											
Physical examination ⁶	X	X	X	X		X		X		X	X
Laboratory safety tests ⁷	X	X	X	X		X		X		X	X
Serology	X										
Urine drug screen, and alcohol and cotinine tests	X	X	X								
Vital signs ⁸	X	X	X	X		X		X		X	X
12-lead safety ECG ⁹	X	X	X	X		X		X		X	X
Pregnancy/FSH test ¹⁰	X	X	X								
OAAS/S and VAS ¹¹			X		X ¹¹						
C-SSRS	X										
PK assessments											
Blood sampling ¹²											
Urine collection ¹³						X ¹³					
Ongoing subject review											
Concomitant medicines											
Adverse events											

Abbreviations: C-SSRS=Columbia-Suicide Severity Rating Scale; ECG = electrocardiogram; FSH = follicle stimulating hormone; FU = follow-up; OAAS = Observer's Assessment of Alertness/Sedation scale; PK = pharmacokinetics; VAS = visual analogue scale.

Notes:

1. Screening will be within 28 days before first dose.

2. Follow up will be 7 (± 2) days after discharge.
3. Height at screening only.
4. Subjects will receive a daily dose of BEN8744 or placebo, by mouth, on Day 1–14. Doses will be given at approximately the same time/s each day (± 15 min from time/s on Day 1). Doses will be taken once or twice daily in the fasted state, unless emerging data indicate they should be taken in the fed state. If BEN8744 will be given twice daily, the last dose will be given in the morning of Day 14.
5. Subjects will be resident on the ward from 1 day before their dose (Day –1) until up to 72 h after final dosing (Day 17).
6. Full physical examinations will be done at screening. Brief (symptom-directed) physical examinations will be done at all other timepoints. On Days 1, 7 and 14, the brief physical examinations should be done before dosing.
7. Laboratory safety tests consist of clinical chemistry, haematology and urinalysis.

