8. Vital signs consist of: supine systolic and diastolic blood pressure, pulse rate, tympanic temperature and respiratory rate. During the period of residence, they will be assessed at the following timepoints on Days 1 and 14: predose, 2, 4, 8 and 12 h postdose. Predose vital signs (including on Days 2–13) should be measured up to 90 min before dosing. If twice-daily dosing, vital signs should be measured before the morning dose only.
9. Triplicate measurements (obtained ≥ 2 min apart) will be made at screening. Single measurements will be made at all other timepoints. Measurements should be made with subjects in a supine position, after resting for 5 min.
10. During the period of residence, ECGs will be recorded at the following timepoints on Days 1 and 14: predose, 2, 4, 8 and 12 h postdose. Predose ECGs (including on Days 2–13) should be done up to 2 h before dosing. If twice-daily dosing, ECGs should be done before the morning dose only.
11. Triplicate ECG recordings (made ≥ 2 min apart) will be made at screening; single recordings will be done at all other timepoints. Recordings should be made with subjects in a supine position, after resting for 5 min.
12. Once-daily dosing: Days 1 and 14 at predose and postdose at 0.25, 0.5, 1, 2, 3, 4, 6, 8, and 12 h; on Days 2 (24 h) and Day 15 (24 and 36 h); on Day 16 (48 h); and on Day 17 (72 h). Trough samples will be taken predose on Days 3, 5, 7, 9, 11, and 13.
13. Twice-daily dosing: Day 1 and 14 at predose, and postdose at 0.25, 0.5, 1, 2, 3, 4, 6, 8, and 12 h (pre-evening dose on Day 1); on Day 1 at 12.5, 13, 14, 15, and 16 h; Days 2 (20 and 24 h) and Day 15 (24 and 36 h); on Day 16 (48 h); and on Day 17 (72 h). Trough samples will be taken pre-morning dose on Days 3, 5, 7, 9, 11, and 13.
14. Blood samples for assay of BEN8744 will be taken on:

 - Once-daily dosing: Days 1 and 14 at predose and postdose at 0.25, 0.5, 1, 2, 3, 4, 6, 8, and 12 h; on Days 2 (24 h) and Day 15 (24 and 36 h); on Day 16 (48 h); and on Day 17 (72 h).
 - Twice-daily dosing: Day 1 and 14 at predose, and postdose at 0.25, 0.5, 1, 2, 3, 4, 6, 8, and 12 h (pre-evening dose on Day 1); on Day 1 at 12.5, 13, 14, 15, and 16 h; Days 2 (20 and 24 h) and Day 15 (24 and 36 h); on Day 16 (48 h); and on Day 17 (72 h). Trough samples will be taken pre-morning dose on Days 3, 5, 7, 9, 11, and 13.

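### Section 11 puts every twice-daily evening dose in Part C after dinner, so the fasted default set elsewhere cannot be followed and steady-state PK would cover only the morning interval

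*Combined protocol and SAP*

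**What the plan says.** Sections 2.6.3 and 8.1.3 and note 4 of section 12.1.3 carry the same rule: "Doses will be taken once or twice daily in the fasted state, unless emerging data indicate they should be taken in the fed state". The Part C opening of section 11 repeats that default, and section 8.5.4 gives the fed or fasted decision to the SRG without limiting it to one of the two daily doses.

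Section 11 then narrows the choice. It introduces the two options with "Therefore, for the morning dose, subjects will either", and adds a separate rule for the other dose: "If subjects are dosed twice daily, they will take their evening doses approximately 1 h after dinner". No exception is given.

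On regimen, section 6.2.4 states that "a twice daily dosage regimen will be required in Part C", although sections 8.1.3 and 8.5.4 still allow once-daily dosing. On the end of dosing, note 4 of section 12.1.3 says: "If BEN8744 will be given twice daily, the last dose will be given in the morning of Day 14". The notes on blood sampling add evening samples on Day 1 only, and "Trough samples will be taken pre-morning dose on Days 3, 5, 7, 9, 11, and 13".

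**The concern.** Two things follow if the SRG keeps the fasted default with twice-daily dosing. First, the regimen that four places describe as the default cannot be carried out, because section 11 feeds subjects before each evening dose. Second, the morning and evening doses are then given under different conditions, but only the morning dose is profiled at steady state.

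This matters for escalation. Section 8.5.4 requires that steady-state C_max and AUC_tau in any individual not be predicted to exceed the maxima seen in Part A, where all doses were fasted. The superposition predictions in sections 6.2.4 and 6.5.2 also rest on fasted Part A profiles. If a post-dinner dose gives higher exposure, the interval that could exceed the maximum is the one not profiled at steady state. The protocol regards fed exposure as uncertain: section 8.1.2 caps the Group B1 dose to guard against unexpectedly high concentrations, and section 6.2.4 suspects saturable gut P-gp and CYP3A4.

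**Working it through.** **Step 1. The prandial rules side by side.**

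| Place | Morning dose | Evening dose |
|---|---|---|
| 2.6.3, 8.1.3, 12.1.3 note 4, section 11 opening | fasted unless data indicate fed | same rule |
| Section 11, detailed rules | fasted or fed, SRG decides | about 1 h after dinner |

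The two rows agree if the SRG chooses fed dosing, since both doses then follow a meal. They conflict if it keeps the default.

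**Step 2. Doses affected.** Dosing runs from Day 1 to the morning of Day 14. Morning doses: 14. Evening doses: 13 (Days 1 to 13). Total: 14 + 13 = 27. Share after dinner: 13/27 = 48%.

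**Step 3. Which doses are sampled.** Counting the twice-daily schedule in section 12.1.3:

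- Day 1, predose to 12 h: 10
- Day 1 evening (12.5, 13, 14, 15, 16, 20, 24 h): 7
- Day 14, predose to 72 h: 14
- Pre-morning troughs: 6

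The sum is 10 + 7 + 14 + 6 = 37, which reproduces Table 16. The once-daily count, 10 + 1 + 14 + 6 = 31, also reproduces Table 16, so the schedule has been read correctly. Of the 37 samples, 7 profile an evening dose after it is given, all on Day 1. None does so on Day 14.

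**Step 4. Does Day 14 carry information on the evening dose?** With a half-life of 2–4 h (section 6.2.4), the fraction of a concentration left after 12 h is 2^(−12/t½): 2^(−6) = 1.6% at 2 h and 2^(−3) = 12.5% at 4 h. Day 14 C_max, AUC_tau, CL_ss/F (dose/AUC_tau) and V_Z/F therefore describe essentially the morning dose. Section 16.1.1 does not say which of the two daily intervals AUC_tau refers to.

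**Step 5. What the Day 1 evening samples can supply.** The 12 h sample and the seven later ones give a full 12–24 h profile. That interval already includes carry-over from the morning dose. What remains from a dose given 24 h earlier is 2^(−24/t½), at most 2^(−6) = 1.6%. If clearance is stable over 14 days, the Day 1 evening interval should be close to the steady-state one. It cannot show a change in clearance over time.

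**Step 6. The 24 h statement.** Section 6.5.2 says the exposure predicted at 140 mg (AUC_24 5,530 ng·h/mL) will not be exceeded in any 24 h period. On twice-daily dosing, AUC_24 is the morning AUC_tau plus the evening AUC_tau, so the morning value alone cannot confirm this. As a threshold only, assume that Table 4's highest-subject prediction at 50 mg BID (4,063 ng·h/mL) splits equally, 2,032 per interval. The evening:morning ratio at which the day reaches 5,530 is (5,530 − 2,032)/2,032 = 1.72. Nothing in the documents says whether the true ratio is above or below this, and 5,530 is itself well under the 24,500 ng·h/mL limit in section 8.5.2.

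**The case against.** The strongest reply has four parts.

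- **Section 10.1 refers the reader to section 11 for fasting requirements, so section 11 governs and the rest is summary.** This lowers the risk of inconsistent conduct. It does not settle the matter, because section 11's own Part C opening sets the fasted default that its evening rule then prevents.
- **Fasted is a default, not an absolute rule.** This is correct. A reader might infer that the other sections simply require fasted doses. They do not, and the fed/fasted mix disappears if the SRG chooses fed dosing.
- **The evening dose is observed.** This is largely correct. A reader might infer that it goes unmeasured, but Day 1 has a full evening profile and the pre-morning troughs follow evening doses. What is missing is an evening profile at steady state; a trough alone gives neither C_max nor AUC.
- **Section 8.5.4 works per dosing interval.** Also correct. A reader might infer that daily exposure will be misstated by doubling the morning AUC_tau. No section plans that, and AUC_24 is not a Part C endpoint, so no error should be charged to it. The narrower point stands: a per-interval check is complete only if it looks at both intervals when their conditions differ.

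Whether the food effect will be known in time is mixed. Section 11 says the SRG decides after reviewing Parts A and B; section 8.1.3 lets Part C run in parallel with Part B. Even with Part B complete, a dose about 1 h after an unspecified dinner is not the fed condition tested in Group B1, so that ratio may not carry over.

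**Conclusion.** The inconsistency is real. Under the fasted default with twice-daily dosing, 13 of 27 doses would follow dinner, and the default regimen could not be given as described. In that case Day 14 PK describes the morning interval only, and the section 8.5.4 check could miss a higher evening interval.

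This rests on two conditions: twice-daily dosing, which section 6.2.4 expects, and the SRG not choosing fed dosing. The direction and size of any morning–evening difference are unknown. The documents do not support a claim that exposure limits would be breached, and the 1.72 threshold above is not an estimate. It is worth correcting before Part C, chiefly because the correction is so cheap.

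**What to change.** 1. Reconcile section 11 with sections 2.6.3, 8.1.3 and 12.1.3 so that one statement governs the prandial state of both daily doses. Which rule is right is for the sponsor and investigator to decide.
2. If morning and evening conditions still differ, derive C_max and AUC(12–24) for the evening interval from the Day 1 samples at 12, 12.5, 13, 14, 15, 16, 20 and 24 h. Report them beside the morning values, and have the SRG consider both intervals in the section 8.5.4 check.
3. State in section 16.1.1 which interval AUC_tau covers, and label Day 14 AUC_tau, CL_ss/F and V_Z/F as morning-interval values.

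The cost is protocol wording and one or two extra derived parameters, with no extra samples. The limitation is that Day 1 evening data only approximate the steady-state evening interval, and the report should say so.

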12.1 Schedules of procedures

12.1.1 *Schedule of procedures (Part A)*

Abbreviations: C-SSRS Columbia-Suicide Severity Rating Scale; ECG = electrocardiogram; FSH = follicle stimulating hormone; FU = follow-up; OAAS/S = Observer's Assessment of Alertness/Sedation scale; PK = pharmacokinetics; VAS = visual analogue scale.

Notes:

1. Screening will be within 28 days before dosing.
2. Follow up will be 7 (± 2) days after discharge.
3. Height at screening only.
4. Subjects will receive a single dose of BEN8744 or placebo in the fasted state, by mouth.
5. Subjects will be resident on the ward from 1 day before their dose (Day -1) until up to 72 h after dosing (Day 4).
6. Full physical examinations will be done at screening. Brief (symptom-directed) physical examinations will be done at all other timepoints.
7. Laboratory safety tests consist of clinical chemistry, haematology, and urinalysis.
8. Pregnancy tests in women of child-bearing potential only. FSH tests in post-menopausal women at screening only.
9. Vital signs consist of: supine systolic and diastolic blood pressure, pulse rate, tympanic temperature and respiratory rate. Triplicate measurements (obtained ≥ 2 min apart) will be made at screening. Single measurements will be made at all other timepoints. Measurements should be made with subjects in a supine position, after resting for 5 min.
10. Triplicate ECG recordings (made ≥ 2 min apart) will be made at screening; single recordings will be done at all other timepoints. Recordings should be made with subjects in a supine position, after resting for 5 min.
11. Subjects will have a 24 h Holter monitor applied during screening and will return the monitor to HMR the following day.
12. Heart rhythm will be monitored continuously (telemetry, 3-lead ECG) from 1 h before until 24 h after dosing.
13. The OAAS/S and VAS will be done immediately before PK blood samples frequently up to 72 h after dosing at the following timepoints: predose and postdose at 0.25, 0.5, 1, 2, 3, 4, 6 and 8 h; on Day 2 (24 h); and on Day 3 (48 h); and on Day 4 (72 h).
14. Blood samples for assay of BEN8744 will be taken on Day 1 at predose and postdose at 0.25, 0.5, 1, 2, 3, 4, 6, 8, 12, and 16 h; on Day 2 (24 and 36 h); on Day 3 (48 h); and on Day 4 (72 h).

When more than one procedure is scheduled at a specific timepoint, procedures should be done in the following order: ECG, vital signs, blood samples (at the scheduled time). Blood sampling should be done on time. Other procedures should be done as close as possible to the scheduled timepoint.

12.1.2 Schedule of procedures (Part B)

Assessment	Day	Screening ¹		Treatment session 1 and 2 ²												FU ³		
		-1	Pre	0	0.25	0.5	1	2	3	4	6	8	12	16	24	36	48	72
Informed consent	X																	
Demography	X																	
Medical history	X																	
Inclusion/exclusion criteria	X	X																
Height and weight ⁴	X	X																
Dose of BEN8744 ⁵													X					
Inpatient visit ⁶																		
Outpatient visit	X																	
Safety assessments																		X
Physical examination ⁷	X	X																X
Laboratory safety tests ⁸	X	X																X
Serology	X																	X
Urine drug screen, and alcohol and cotinine tests	X	X																X
Vital signs ⁹	X	X	X										X	X	X	X	X	X
12-lead safety ECG ¹⁰	X		X									X	X	X	X	X	X	X
Pregnancy/FSH test ¹¹	X	X																X
C-SSRS	X																	X
OAAS/S and VAS ¹²													X	X	X	X	X	X
Pharmacokinetic assessments																		
Blood sampling ¹³																		
Urine and faecal sample collection ¹⁴													X	X	X	X	X	X
Ongoing subject review																		
Adverse events																		
Concomitant medication																		

Abbreviations: C-SSRS Columbia-Suicide Severity Rating Scale; ECG = electrocardiogram; FSH = follicle stimulating hormone; FU = follow-up; PK = pharmacokinetics; VAS = visual analogue scale.

Notes:

1. Screening will be within 28 days before first dose.
2. Each subject will have 2 study sessions, with a washout period of at least 7 days between doses.

3. Follow up will be 7 (± 2) days after discharge in Session 2.
4. Height at screening only.
5. Subjects will receive a single dose of BEN8744, by mouth, in each session: 1 in the fasted state, and 1 in the fed state.
6. Subjects will be resident on the ward from 1 day before their dose (Day -1) until up to 72 h after dosing (Day 4).
7. Full physical examinations will be done at screening. Brief (symptom-directed) physical examinations will be done at all other timepoints.
8. Laboratory safety tests consist of clinical chemistry, haematology and urinalysis.
9. Vital signs consist of: supine systolic and diastolic blood pressure, pulse rate, tympanic temperature and respiratory rate. Triplicate measurements (obtained ≥ 2 min apart) will be made at screening. Single measurements will be made at all other timepoints. Measurements should be made with subjects in a supine position, after resting for 5 min.
10. Triplicate ECG recordings (made ≥ 2 min apart) will be made at screening; single recordings will be done at all other timepoints. Recordings should be made with subjects in a supine position, after resting for 5 min.
11. Pregnancy tests in women of child-bearing potential only. FSH tests in post-menopausal women at screening only.
12. The OAAS and VAS will be done immediately before PK blood samples frequently up to 72 h after dosing at the following timepoints: predose and postdose at 0.25, 0.5, 1, 2, 3, 4, 6 and 8 h; on Day 2 (24 h); and on Day 4 (72 h).
13. Blood samples for assay of BEN8744 will be taken on Day 1 at predose and postdose at 0.25, 0.5, 1, 2, 3, 4, 6, 8, 12 and 16 h; on Day 2 (24 and 36 h); on Day 3 (48 h); and on Day 4 (72 h) in each treatment session.
14. Continuous urine and faecal sample collection for exploratory characterisation of BEN8744 and its metabolites will be taken after dosing on Day 1 at 0–12 h, 12–24 h, 24–48 h, and 48–72 h.
A urine spot sample will be taken before dosing on Day 1.
A predose faecal sample will be collected from Day -2 to predose on Day 1 in Part B Session 1.

When more than one procedure is scheduled at a specific timepoint, procedures should be done in the following order: ECG, vital signs, blood samples (at the scheduled time). Blood sampling should be done on time. Other procedures should be done as close as possible to the scheduled timepoint.

